**d. Study Endpoints:**

Albert Einstein Healthcare Network <hr/> Einstein	AEHN Protocol/Summary		
	NUMBER	DATE	PAGE
	HRP-204	11/1/2011	10 of 27

- i. Describe the primary and secondary study endpoints (*i.e. the outcome(s) that the study is designed to evaluate*): Overall, the study will examine motor functioning of the impaired arm as well as sensation in the limb as well as hemispatial neglect (participants with right hemisphere lesions only). The primary outcome measures will be the (1) upper extremity portion of the Fugl-Meyer test, a standard clinical measure of arm motor impairment, (2), Action Research Arm Test (ARAT), a valid and reliable measure of arm function in simulated ADLs, (3) the Rivermead Assessment of Somatosensory Performance (RASP), which tests proprioception, two-point discrimination, surface pressure touch, surface localization, and tactile extinction [121], and (4) in right hemisphere patients only, a virtual-reality assessment of navigation (VRLAT) developed by [name] [77], which is more sensitive to mild forms of hemispatial neglect than paper-and-pencil tests. Secondary outcome measures will be (1) the Stroke Impact Scale, a self-report measure of use of limb in activities of daily living (2) timed finger tapping, (3) maximum grip and pinch force, as assessed using a dynamometer, and (4) the Wolf Motor Function Test [78] to assess function limitations and allow comparison with the results of CIMT (used as a secondary measure because patients with lower Fugl-Meyer score will not be able to complete many items on this test).
- ii. Describe any primary or secondary safety endpoints (*e.g. any disease or symptom that would result in the withdrawal of that subject from the study*): N/A

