#### e. Human Research Methods:

- i. Describe and explain the study design (*e.g. randomized, double-blind, placebo-controlled clinical trial or retrospective chart review*): randomized, placebo-controlled clinical trial
- ii. Describe all research activities involved in this protocol, including a study visit timeline if appropriate: C.5. PRE-TREATMENT ASSESSMENT: Should the patient meet the inclusion criteria, an additional battery of pre-treatment assessment tests will be completed as the first measure of the primary and secondary outcome measures. The primary outcome measures will be the (1) Fugl-Meyer test, described above, (2), Action Research Arm Test (ARAT), a valid and reliable measure of arm function in simulated ADLs, (3) the Rivermead Assessment of Somatosensory Performance (RASP), which tests proprioception, two-point discrimination, surface pressure touch, surface localization, and tactile extinction [121], and (4) in right hemisphere patients only, a virtual-reality assessment of navigation (VRLAT) developed by [name] [77], which is more sensitive to mild forms of hemispatial neglect than paper-and-pencil tests. Secondary outcome measures will be (1) Stroke Impact Scale [76], (2) timed finger tapping, (3) maximum grip and pinch force, as assessed using a dynamometer, and (4) the Wolf Motor Function Test [78] to assess function limitations and allow comparison with the results of CIMT (used as a secondary measure because patients with lower Fugl-Meyer score will not be able to complete many items on this test). Finally, the confirmatory behavior tests listed in Table 1 will be included in the pre-treatment assessment (see B.4 for details). We anticipate that the full pre-treatment screening can be completed in 2 90-minute sessions. De-identified data from both the inclusion screening and pre-treatment assessment will be discussed with the PI before brain scanning is undertaken (C.6) and the patient is assigned to a therapy group

Albert Einstein Healthcare Network <hr/> Einstein	AEHN Protocol/Summary		
	NUMBER	DATE	PAGE
	HRP-204	11/1/2011	11 of 27

(C.7.a) to ensure that the patient meets inclusion criteria and that no unusual combination of scores might suggest errors in data collection or scoring.

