#### C.7. THERAPY REGIMEN

**a. Group assignment:** A research assistant (RA), who will not be involved in any assessments, will assign patients to the MT or placebo therapy (identical therapy with an opaque divider rather than a mirror) using stratified randomization based on the patient's Fugl-Meyer score. Before starting the trial an assignment order will be developed based on whether a patient's pre-treatment Fugl-Meyer score was low (between 10 and 30) or moderate (between 30 and 50). A previous MT RCT using a similarly chronic patient population and an identical placebo therapy showed little benefit of the placebo therapy. Thus, we must consider a balance between the scientific requirements of an appropriate control group and the ethical considerations of using patients' time to complete a therapy that is known to be ineffective. To balance these considerations, we will assign patients to the MT and placebo treatment groups in a 2:1 ratio, respectively. This inequality in sample size will only reduce statistical power by approximately 3% [81]. In addition, patients assigned to placebo treatment will be given the option of being crossed over to receive MT after the three month assessment. Patients will not be aware of which therapy is the placebo because both therapies will be described as studying the role of visual feedback rather than a test of "mirror therapy." Both treatments will include 2 daily 30 minute

Albert Einstein Healthcare Network <hr/> Einstein	AEHN Protocol/Summary		
	NUMBER	DATE	PAGE
	HRP-204	11/1/2011	12 of 27

therapy sessions, 5 days per week over a 4 week period.

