#### **g. Data Management**

Albert Einstein Healthcare Network <hr/> Einstein	AEHN Protocol/Summary		
	NUMBER	DATE	PAGE
	HRP-204	11/1/2011	15 of 27

i. Describe steps that will be taken to secure the data (e.g. training, authorization of access, password protection, encryption, physical controls, certificates of confidentiality and separation of identifiers and data) during storage, use and transmission: All computerized data will be password and stored only on the network share drive.

ii. Describe the data analysis plan, including any statistical procedures and method for determining the sample size for the study: C.11. Testing Specific Aim 1 (benefit of home-based MT)

Tests for improvement in the primary and secondary outcome measures (see C.4) administered during the pre-treatment assessment and the two post-treatment assessments will be separately compared using ANCOVA analyses with post-treatment values as DVs, therapy type (MT, placebo) as the IV, and pre-treatment assessment score as the covariate [74]. Confirmation of MT's benefit will be tested in the main effect of therapy type.

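### Randomisation is stratified by Fugl-Meyer, but the C.11 ANCOVA omits baseline Fugl-Meyer for every outcome except Fugl-Meyer itself, at some cost in precision

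*Combined protocol and SAP*

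**What the plan says.** Section 6.e.ii, C.7.a, assigns patients 2:1 to mirror therapy or placebo "using stratified randomization based on the patient's Fugl-Meyer score", with two strata described as "low (between 10 and 30) or moderate (between 30 and 50".

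Section 6.g.ii, C.11, says the primary and secondary outcomes "will be separately compared using ANCOVA analyses with post-treatment values as DVs", with "therapy type (MT, placebo) as the IV, and pre-treatment assessment score as the covariate". It adds: "Confirmation of MT's benefit will be tested in the main effect of therapy type". The natural reading of the single covariate is each outcome's own baseline value.

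Section 6.d.i lists four primary outcomes: Fugl-Meyer, ARAT, RASP and, in right-hemisphere patients only, VRLAT. The secondary outcomes are the Stroke Impact Scale, finger tapping, grip and pinch force, and the Wolf Motor Function Test. Only the first primary outcome has the stratifier as its own baseline.

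C.5 makes the Wolf test secondary because "patients with lower Fugl-Meyer score will not be able to complete many items on this test".

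**The concern.** A variable that was important enough to stratify on would normally also be in the analysis model. Stratification makes the arms more alike on Fugl-Meyer than chance would. A model that ignores the variable still counts its contribution as noise. If Fugl-Meyer carries information about an outcome beyond that outcome's baseline, two things follow: the reported standard error overstates the true sampling error, and real precision available from the covariate is not used.

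The omission does not look like shorthand. The lesion analysis in C.13.a names a second covariate, total lesion volume, where one is wanted. No section adds the stratum or baseline Fugl-Meyer to the Aim 1 models. What is at stake is power, in a trial of 100 patients split 2:1. A related wording point is that a score of 30 belongs to both strata as printed.

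**Working it through.** **The plan's own power figure.** C.7.a puts the power loss from 2:1 allocation at about 3%. With 100 patients, the variance relative to 1:1 is (1/66.7 + 1/33.3) / (1/50 + 1/50) = 0.045/0.04 = 1.125. At an assumed two-sided 5% level, power of 80, 85, 90 or 95% at 1:1 falls by 4.8, 4.4, 3.7 or 2.5 points. The stated figure is broadly reproduced (the plan gives no base power) and is a useful yardstick.

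**Inputs for the omitted covariate.** From the documents: n = 100, 2:1 allocation, two Fugl-Meyer strata, eligible scores 10 to 50. Assumed, because the documents give no values: Fugl-Meyer uniform on 10–50; strata 10–30 and 31–50; blocks of 6; correlation 0.7 between Fugl-Meyer and the outcome's own baseline; own-baseline coefficient 0.8; residual SD 0.5; Fugl-Meyer coefficient b = 0 to 0.3 per SD; treatment effect 0.30 on the same scale.

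**What b means as a partial correlation.** The SD of Fugl-Meyer given the own baseline is √(1 − 0.7²) = 0.714, so r = 0.714b / √((0.714b)² + 0.5²).
- b = 0.1: r = 0.14
- b = 0.2: r = 0.27
- b = 0.3: r = 0.39

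Before the cost of a degree of freedom, the reported variance should fall by a factor of 1/(1 − r²): about 1.08 at b = 0.2 and 1.18 at b = 0.3.

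**Simulation, 10,000 trials per case.**

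| | b = 0.1 | b = 0.2 | b = 0.3 |
|---|---|---|---|
| Mean reported SE: planned | 0.1073 | 0.1105 | 0.1156 |
| with stratum | 0.1069 | 0.1081 | 0.1102 |
| with continuous Fugl-Meyer | 0.1066 | 0.1065 | 0.1066 |
| Actual SD of estimate: planned | 0.1076 | 0.1084 | 0.1121 |
| with stratum | 0.1075 | 0.1076 | 0.1100 |
| with continuous Fugl-Meyer | 0.1072 | 0.1056 | 0.1065 |
| Power: planned | 79.1% | 77.1% | 72.7% |
| with stratum | 79.2% | 78.5% | 76.1% |
| with continuous Fugl-Meyer | 79.6% | 79.6% | 78.9% |
| Type I error: planned | 5.1% | 4.4% | 4.2% |

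As variance ratios against the planned model, continuous Fugl-Meyer gives 1.014, 1.075 and 1.177 for the reported variance, and 1.007, 1.054 and 1.106 for the actual variance. The stratum indicator gives 1.008, 1.044 and 1.101, and 1.002, 1.015 and 1.037. The planned model's mean estimate under no effect stays within 0.002 of zero.

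**Hand check at b = 0.3.** The planned test rejects above 1.985 × 0.1156 = 0.2295, and (0.30 − 0.2295)/0.1121 = 0.63, giving power of about 73.5%. With Fugl-Meyer the limit is 1.985 × 0.1066 = 0.2116, and (0.30 − 0.2116)/0.1065 = 0.83, giving about 79.7%. Both are close to the simulated values.

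**Cost if Fugl-Meyer adds nothing (b = 0).** The reported variance ratio is 0.994 at n = 100, a loss of about 0.6%, or 0.2 to 0.3 of a power point. At an assumed n = 50 for a subset such as VRLAT, it is 0.986, a loss of about 1.4%.

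**Second set-up.** This used n = 99, blocks of 3, 6,000 runs per case, and correlation 0.2 or 0.8 between Fugl-Meyer and the own baseline. The residual variance given the own baseline was held fixed, so planned power stays near 78–80%. Power, planned against continuous Fugl-Meyer:
- r = 0.2: 78.3–78.4% against 79.4–79.8%
- r = 0.3: 78.6–79.0% against 81.2–82.3%
- r = 0.5: 79.4–80.3% against 88.2–88.5%

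At r = 0.5 the planned test's type I error was 3.0–4.3%.

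**The case against.** The best reply is that nothing here is an error. The planned ANCOVA already adjusts for each outcome's own baseline, it is unbiased, and a second covariate is a matter of choice. The loss exists only if Fugl-Meyer predicts an outcome beyond its own baseline, and the documents do not show that it does. The remark about the Wolf test shows an association with Fugl-Meyer. A patient who cannot complete the items after treatment may have been unable to before it, and the planned covariate would record that. For RASP (sensation) and VRLAT (neglect) there is little reason to expect a gain, and VRLAT's smaller sample is where an unneeded covariate costs most. The stratum indicator alone also recovers slightly more than half of the power: 1.4 of 2.5 points at b = 0.2 and 3.4 of 6.2 at b = 0.3.

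Much of this stands. The size cannot be established from the documents, and it may be nil for some outcomes. But the trade is lopsided: a fraction of a power point at risk with 100 patients, against a possible gain of several points. One rule for all outcomes also avoids choosing covariates outcome by outcome. The stratum indicator's power comes largely from correcting the overstated standard error. It delivers only 0.015 of 0.054, or 0.037 of 0.106, of the reduction in actual variance. That comparison does depend on the assumed linear effect and uniform scores.

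**Conclusion.** The concern holds as a modest efficiency point that should be addressed. Outside the Fugl-Meyer outcome, the C.11 model omits the variable that the trial randomises by. There is no bias and no inflation of the false-positive rate; where Fugl-Meyer matters, the planned test is slightly conservative.

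Under the stated assumptions, the gain from adding it runs from marginally negative (no added prediction), through about half a power point (b = 0.1), to about 2.5 and 6 points (b = 0.2 and 0.3). At the upper end this is similar to or larger than the 3% loss that C.7.a thought worth justifying. A gain is more plausible for the arm-motor outcomes (ARAT, Wolf, grip and pinch force, tapping) than for RASP or VRLAT. The overlap at a score of 30 is a wording matter and adds no weight.

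**What to change.** In C.11, prespecify baseline Fugl-Meyer as an additional continuous covariate in the ANCOVA of every outcome other than Fugl-Meyer, whose own baseline already covers it. The continuous score is preferable to the two-level stratum, and the model then does not depend on where the strata are cut. The choice should be written down before outcome data are seen, because a covariate added afterwards is open to challenge.

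Separately, reword C.7.a so that a score of 30 falls in exactly one stratum.

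The cost is one degree of freedom per model and two small text changes. Baseline Fugl-Meyer is an eligibility measure, so every randomised patient has it. Visits, data collection and sample size do not change.

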**C.12. Testing Specific Aim 2 (optimal treatment dosing)**

Optimal treatment dosing will be examined by expressing each primary outcome measure's average value at the three mid-treatment assessments and the three-month post-treatment assessment as a percentage between pre-treatment (0%) and immediate post-treatment (100%) assessments. This information could then be used in clinical decision-making when determining whether the magnitude of change expected in a given time period would be "worth" the additional treatment time or whether that addition time would be better spent trying another therapy. Inferential tests will not be used because of the problem of being unable to detect "non-significant" differences between two time points as well as the possibility that the large sample size will be able to detect statistically-significant differences across adjacent time points even though the clinical significance of the differences' magnitudes are questionable.

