**1) Protocol Abstract** (*Briefly (in 250 words or less) describe the study in language understandable to a layperson. Include a brief description of the study purpose, target disease/condition if applicable, key eligibility criteria, and main study interventions*): Each year in the United States 550,000 people develop upper-extremity movement deficits after stroke (hemiparesis). The recent success of mirror therapy (MT) is notable because it is a simple treatment for hemiparesis, and may be feasible for home use. MT uses a standard mirror to create a compelling illusion in which movements of the unimpaired limb appear as if they are being made by the impaired limb. We propose to complete a randomized placebo-controlled clinical trial of home-based MT with a target enrollment of 100 chronic stroke patients. The therapy will consist of a standardized set of hand, wrist, and elbow movements completed in two daily 30-minute sessions, 5 times per week for 4 weeks. Patients assigned to the placebo treatment (identical therapy with an opaque divider rather than a mirror) will be crossed over to receive MT after a three month follow-up. The therapy will be performed by the participant within his/her home. This project will have two phases. The first phase, to be completed at Einstein, will include all of the behavioral testing. The second phase, to be completed at the University of Pennsylvania, will be limited to MRIs and CTs and will be completed under a separate IRB protocol at the University of Pennsylvania with [name] at the site PI.

**2) Project Objectives and Hypotheses:** The first goal of the study will be to determine whether a home-based form of MT is an effective treatment of hemiparesis. The second goal will be to determine the optimal dosing of MT by including weekly measures of improvement. The third goal will be to understand individual differences in the efficacy of mirror therapy. Previous MT studies have not reported, or lacked the power to test, why some patients benefit from MT and others do not, even though significant individual differences have been reported. Our use of a large sample of patients will allow us to assess predictors of therapeutic benefit.

Albert Einstein Healthcare Network <hr/> Einstein	AEHN Protocol/Summary		
	NUMBER	DATE	PAGE
	HRP-204	11/1/2011	2 of 27

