assigned to the placebo treatment (identical therapy with an opaque divider rather than a mirror) will be crossed over to receive MT after a three month follow-up. To date 7 patients have completed the proposed therapy regimen in a pilot study, and overall the results were encouraging. Patients showed an average improvement (relative to baseline) of 27% and 24% on the Wolf Motor Function test and Jebsen Hand Function test, respectively, two functional tests of simulated ADL performance. Even greater improvements were observed at the impairment level, with average improvement on grip force, pinch force, and finger tapping being 63%, 58%, and 43%, respectively. If the results of the full trial match those of the pilot study, home-based MT would be a meaningful advancement in the cost of hemiparesis rehabilitation.

Reduced medical costs could also come from more efficient therapist utilization. Because the therapeutic benefits of rehabilitation often decrease over time, it would be worthwhile to know the balance between treatment dosing and treatment benefit. To date little is known about the dosing of MT because only one study [18] has measured therapeutic benefit at multiple time points during treatment (in contrast to only before and after 4 or 6 weeks of treatment in previous RCTs [15, 20, 21]). Stevens and Stoykov [18] reported that two chronic stroke patients given 12 1-hour sessions of MT improved most rapidly after 3 sessions (the first assessment point) and showed relatively minor improvement in the following 7 sessions (the second assessment point). These case studies suggests that reducing dosage of MT could still lead to a clinically significant improvement in functioning. The proposed study would inform the issue of MT dosing by measuring outcomes after each week of treatment in a large sample of patients. Our pilot study results indicate that most of MT's therapeutic benefit may occur within the first two weeks of treatment. In this study we administered three impairment level tests (grip force, pinch force, finger tapping) as well as the Jebsen test after each week of therapy. Average improvement was 21%, 44%, 46%, and 47% for weeks 1-4, respectively. Although additional data are clearly needed to further support this claim, these initial results suggest that reduced therapy dosing may be nearly as therapeutic as longer courses of treatment.

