b. Training therapies: Therapy instructions for both treatment groups will be presented using the same DVD shown using a portable DVD player. The 30 minute video will consist of 2 repetitions of a set of 15 movements including flexion and extension of the thumb, index, and middle fingers, opening and closing the hand, pinch grip with the thumb and index fingers, sequences of finger movements, wrist movement (pronation/supination, flexion/extension, radial/ulnar deviation), and flexion and extension at the elbow. Each trained movement will first be shown to the patient 3 times, after which the screen will go blank to allow the patient to focus on viewing their movements rather than the video monitor. A metronome sound will be presented on the video at 30 bpm and patients will be instructed to move in time with it. The metronome will run for 1 minute and 45 seconds followed by a 15 second rest break, after which the next movement will be presented. Instructions on the video will remind participants to make the same movement with both limbs "as well as possible" [19].

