C.8. MID-TREATMENT ASSESSMENTS: Three mid-treatment assessments will be performed, one immediately before every 5th day of therapy (before start of day 6, 11, and 16; see C.7.c), and will include only the primary outcome measures. The assessors will be unaware of group assignment, and before each session the assessor will remind patients to avoid mentioning any details of their therapy. The assessor will be given a questionnaire at the end of each assessment concerning the treatment to which they believe the patient has been assigned.

C.9. POST-TREATMENT ASSESSMENTS: The two post-treatment assessments (1 day and 3

Albert Einstein Healthcare Network  Einstein	AEHN Protocol/Summary		
	NUMBER	DATE	PAGE
	HRP-204	11/1/2011	13 of 27

months after final treatment session) will test both primary and secondary outcome measures. Procedures will be identical to mid-treatment assessments. To maximize retention at 3 months, the research assistant will make monthly calls to participants to maintain contact with the patient and be aware of any upcoming scheduling issues that might prevent timely follow-up.

- iii. Identify which tests/procedures are being administered solely for research purposes and which are being conducted as part of standard of care (i.e. procedures that would be done even if the participant were not involved in research): All tests are solely for research purposes. As a summary these tests are the screening tests (Fugl-Meyer, Western Aphasia Battery comprehension test, clinical hemianopia test, spatial action recognition test, Parson's test of hand laterality decisions, imagined grasping of objects) and assessment tests (Fugl-Meyer, Action Research Arm Task, Rivermead Assessment of Somatosensory Performance (RASP), virtual reality laterized attention task, Stroke Impact Scale, timed finger tapping, maximum grip and pinch force, Wolf motor function task) and brain scans (MRI or CT). Brain scanning (both MRIs and CTs) will be completed under a separate IRB protocol at the University of Pennsylvania with [name] as the site PI.

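### The Aim 2 weekly dosing curve is planned with no measure of precision and makes no use of the concurrent placebo arm

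*Combined protocol and SAP*

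**What the plan says.** The second goal, in section 2 (Project Objectives and Hypotheses), is to "determine the optimal dosing of MT by including weekly measures of improvement". Its only analysis is C.12. There, each primary outcome's average at the three mid-treatment visits and at 3 months is expressed "as a percentage between pre-treatment (0%) and immediate post-treatment (100%) assessments". The curve is meant to help clinicians judge whether further weeks of treatment are worthwhile. C.12 rules out inferential tests, because a non-significant difference between time points is hard to interpret and a significant one may be clinically trivial. It mentions no interval, names no arm and plans no comparison with placebo.

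The arms are compared in C.11, where outcomes "administered during the pre-treatment assessment and the two post-treatment assessments will be separately compared using ANCOVA analyses", that is, at 1 day and 3 months. C.13 uses the MT group only and post-treatment scores. Nothing else in the plan analyses weeks 1-3.

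The data for a weekly comparison will nevertheless exist. The C.8 visits "will include only the primary outcome measures", are not limited to the MT arm, and use assessors who do not know the assignment. Under C.7.a, placebo patients can cross over only after the 3-month assessment.

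**The concern.** A percent-of-final curve is a ratio of two estimated mean changes, and its denominator is uncertain too. Without an interval, a clinician cannot tell a real plateau at week 2 from a share that could well be much lower. C.12's objections are to significance tests; they do not apply to intervals, which show the range of magnitudes that C.12 itself wants judged.

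Secondly, C.7.b states: "Therapy instructions for both treatment groups will be presented using the same DVD". Gains from the exercises, or from repeated testing, could therefore occur in both arms and would remain in an MT-only curve. C.11 shows whether MT beats placebo after treatment; no planned analysis looks at this during treatment.

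What is at stake is the credibility of any statement that a shorter course gives most of the benefit. The Aim 1 test is not at stake.

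**Working it through.** **Inputs.** From the documents: 100 patients (section 5.b) at 2:1 (C.7.a), so about 67 MT and 33 placebo; and the pilot time course in A.2, "Average improvement was 21%, 44%, 46%, and 47% for weeks 1-4, respectively" (7 patients; average over grip, pinch, finger tapping and Jebsen, none of them a primary outcome). Assumed, because the documents give no figure: the size of the total change in units of the SD of change, the between-week correlation, the placebo gains, and no dropout. Pilot week 4 stands in for the 1-day value.

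**1. The pilot on the C.12 scale.** 21/47 = 44.7%, 44/47 = 93.6%, 46/47 = 97.9%, 47/47 = 100%.

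**2. Precision of the week-2 share within MT.** Let s = 44/47 = 0.936 be the share, d the total change in SDs of change, r the between-week correlation and n = 67. With equal SDs, the approximate variance of the ratio is (1 + s² − 2sr)/(n·d²).
- r = 0.7, d = 1.0: (1 + 0.876 − 1.311)/67 = 0.0084. The standard error is 0.092 and the 95% half-width 1.96 × 0.092 = 0.18, giving about 76-112%.
- r = 0.7, d = 0.5: the half-width doubles to 0.36, giving about 58-130%.

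The ratio is skewed, so simulated percentiles are better (400,000 sets of four weekly mean changes, pilot-shaped means, equal SDs, equal correlations):

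| Total change | r = 0.6 | r = 0.7 | r = 0.8 | r = 0.9 |
|---|---|---|---|---|
| 0.5 SD | 55-152% | 59-142% | 64-132% | 71-119% |
| 1.0 SD | 74-117% | 76-114% | 79-110% | 83-105% |

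**3. Sensitivity to the SD assumption (r = 0.7).** If the SD of change grows with the mean change instead of being equal across weeks:

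| Share | Total change | Equal SDs | SD proportional to mean change |
|---|---|---|---|
| Week 1 | 0.5 SD | -5 to 79% | 29-68% |
| Week 1 | 1.0 SD | 24-62% | 37-54% |
| Week 2 | 0.5 SD | 59-142% | 62-143% |
| Week 2 | 1.0 SD | 76-114% | 77-113% |

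The week-2 result is robust to this choice; the week-1 result is not.

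**4. Effect of placebo gain on the curve.** Net share = (pilot week w − placebo week w)/(47 − placebo week 4).
- Flat gain of 2 to 5 points: week 1 from (21−2)/(47−2) = 42.2% to (21−5)/(47−5) = 38.1%; week 2 from 93.3% to 92.9%.
- Linear gain reaching 2 to 5 points: week 1 from (21−0.5)/45 = 45.6% to (21−1.25)/42 = 47.0%; week 2 from 95.6% to 98.8%.
- Zero gain, or gain proportional to MT's: no change.
- A large shift needs a large gain. At 20 points, week 1 is (21−20)/27 = 3.7% (flat) or (21−5)/27 = 59.3% (linear).

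**5. What a weekly contrast could deliver.**
- Half-width at one week, unadjusted: 1.96 × √(1/67 + 1/33) = 0.42 SD of change, against 1.96/√67 = 0.24 SD for the MT mean.
- Half-width for a week-to-week change in the contrast, r = 0.7: 1.96 × √(2 × 0.3) × √(1/67 + 1/33) = 0.32 SD.
- Pilot-shaped steps with no placebo gain: 0.24, 0.02 and 0.01 SD for a total of 0.5 SD; 0.49, 0.04 and 0.02 SD for 1.0 SD. Only the week 1-2 step at 1.0 SD exceeds 0.32.
- A percent curve formed from the contrast would be unstable: in simulation, its week-2 share spans about 17-233% at 0.5 SD and 64-134% at 1.0 SD (r = 0.7, no placebo gain).

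**The case against.** Aim 2 is descriptive by a reasoned choice. Expected total change on MT is a sensible quantity for a clinician deciding whether to continue, and C.11 already tests whether MT beats placebo. Since the goal concerns MT dosing, an MT-only curve is the natural reading although C.12 names no arm. C.7.a reports that an earlier trial with an identical placebo "showed little benefit of the placebo therapy", and placebo gains of that order hardly move the curve. Weekly contrasts would rarely date the separation of the arms.

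All of this stands, and it limits the point. It does not answer the lack of precision, which remains even if placebo gain is exactly zero. The expectation of little placebo benefit rests on earlier evidence that the weekly data could check.

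A reader might infer more: that gains shared with placebo make the dosing curve misleading, or that the plan leaves MT's benefit uncontrolled. The documents support neither. The first needs a placebo gain of around 20 points, which C.7.a gives no reason to expect; the second overlooks C.11. A reader might also infer that C.12 forbids intervals. It excludes tests and is silent on intervals.

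**Conclusion.** The concern holds as a gap in reporting and estimation for Aim 2. The only analysis of weeks 1-3 gives clinicians a percent curve without precision and leaves the concurrent placebo data unused. Imprecision is the main part: under the assumptions shown, the week-2 share could not be told apart from a clearly lower one at a total change of 0.5 SD, and even in the most favourable case examined (1.0 SD, correlation 0.9) it spans 83-105%. The week-1 range is wide or moderate depending on the SD assumption. Distortion by common gains is a lesser, checkable possibility. All sizes rest on assumed effect sizes and correlations and on a 7-patient pilot in other outcomes. No error rate, sample size or Aim 1 result changes.

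**What to change.** In C.12, for each primary outcome (VRLAT in right-hemisphere patients only):
- compute the percent-of-1-day curve within the MT arm, with a bootstrap 95% CI;
- show the placebo arm's weekly means separately, in outcome units;
- report the baseline-adjusted MT-minus-placebo difference with 95% CI at weeks 1, 2 and 3, as estimation without significance tests. One repeated-measures model per outcome, with baseline score, therapy, visit and therapy-by-visit, would supply these.

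Do not form the percent curve from the contrast. C.11 stays as the Aim 1 test.

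**Cost.** Some wording and four models; no added visits or patients. The contrast intervals will be wide: at most about ±0.42 SD of change with no dropout (narrower with baseline adjustment), or 0.42/√0.8 = ±0.47 with an assumed 20% dropout. For VRLAT the unadjusted figure is about 0.42/√0.5 = ±0.59 SD if half the patients have right-hemisphere lesions (assumed). The text should say that these contrasts can reveal a placebo gain large enough to distort the curve materially, but will usually not establish when the MT-placebo difference arises. The dosing claim becomes more modest.
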